validity. Scores can range from 0-6, with scores of 1-4 indicative of possible depression and scores of 5-6 indicating probable depression.

d. Causal attribution assessments.¹¹ Sentinel health events may be associated with changes in smoking behavior. These may include a visit to an ED for a tobacco-related illness, hospital admission, or surgery. Patients who perceive their acute health events as related to tobacco use are more likely to quit, as we found in our pilot trial. We will therefore assess patients' beliefs re: the proximate reasons for their ED visit, using a 2-item measure co-developed by [name].

e. Wisconsin Predicting Patients' Relapse Questionnaire (WI-PREPARE).⁵⁸ This 7-item scale will be used to assess patient's likelihood of a relapse to smoking, after the ED visit. Two items of the WI-PREPARE, assessing time to first cigarette and daily consumption, constitute the Heavy Smoking Index (HSI), a subscale of the Fagerström Test for Nicotine Dependence (FTND).^{47,59} The HSI, a measure of the severity of nicotine dependence, will be used to guide the dosing of NRT.

f. Biochemical assessment. Exhaled carbon monoxide (CO) levels will be measured for each enrollee with the Bedfont Smokerlyzer. CO will be measured again at 3 months for subjects self-reporting tobacco abstinence. Subjects endorsing abstinence by phone will be asked to return to the ED, or a mutually convenient location in New Haven, for CO measurement. *In our last trial, 92/97 (94%) such subjects returned.*

h. Rapid Alcohol Problems Screen (RAPS). The RAPS is a 4-item tool designed specifically for detecting problematic alcohol use in medical settings, and it has been well-validated for use in the ED setting.^{62,63} A "yes" response on any of the items places the participant in the "likely" group. The RAPS has demonstrated good reliability and validity when validated against ICD-10 and DSM-IV criteria for alcohol abuse or dependence, with an average sensitivity of 93% and specificity of 87%. It generally outperforms other alcohol screening measures like the CAGE and the AUDIT in terms of test characteristics.⁶³

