Sample size and power calculations. The goal of this proposal is to identify individual tobacco dependence treatment interventions which show clinical efficacy, subject to constraints of cost effectiveness and acceptability. *As each component is allocated to half the participants, the sample size to detect main effects in a full factorial MOST design is not depending on the number of components evaluated, but rather the smallest clinically important difference between the presence and absence of a component.* In our previous trial, we found a difference of 7.3% in biochemically confirmed abstinence between the control and intervention arms at 3 months. It is reasonable to expect that, in this factorial trial, the effect of individual components will be less than that seen in the multicomponent trial.^{13,69} Therefore, we have chosen an absolute difference of 5% for the main effects of each component. (We considered a narrower absolute difference of 4%, but the sample size and resources needed become unfeasible.) With a two-sided 0.05 significance level, and an average abstinence proportion of 4.9% in the absence of a component, a total sample size of 860 participants will provide 80% power to detect a 5% increase in the abstinence rate. We will enroll **1056** participants to account for up to a 15% dropout rate by 3 months. *Although we will investigate whether the effect of a component is dependent on the levels of other components (i.e. interactions) our trial has not been powered with the intent to detect these interactions.*

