Analysis for Aim 1. The primary outcome, abstinence at 3 months, will be compared between the presence and absence of each component using logistic regression. Per convention, in the primary analysis missing abstinence data will be imputed as relapse. For this full-factorial design, the model will include main effects for each of the 4 components as well as all 2, 3 and 4-way interactions. The regression will also include baseline covariates: age, sex, race/ethnicity, and smoking characteristics. Main effects will be evaluated at the 0.05 significance level. Differences in proportions for the presence and absence of each component (i.e. main effects)

will be estimated along with 95% confidence intervals using the bootstrap method.⁷⁴ A p-value of 0.10 will be used as a guide to flag potentially important interactions which will be explored graphically with a particular emphasis on identifying substantial synergistic effects or qualitative (i.e. where the impact of one component changes direction depending on the presence or absence of another component) effect modification. Similar analyses will be performed at 1-month follow-up. Additionally, a logistic regression with parameters estimated by weighted Generalized Estimating Equations (GEE) will incorporate both 1 and 3-month outcome data without imputing non-responders as relapse.⁷⁵ This analysis weights for the probability of response and is valid under the assumption that missing data are missing at random (MAR). Secondary outcomes at 1 and 3 months will also be evaluated by a generalized linear model with weighted GEE.

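### The protocol reports that seeing the ED visit as tobacco-related predicted quitting and collects that score at baseline, but the primary model's covariate list omits it; adding it would give a small gain in power

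*Combined protocol and SAP*

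**What the plan says.** Section V.12, item 8, Analysis for Aim 1, specifies a logistic regression of 3-month abstinence on the four components and all their interactions. It adds: "The regression will also include baseline covariates: age, sex, race/ethnicity, and smoking characteristics". The smoking characteristics are not itemised there or elsewhere. Differences in proportions for each component are to be reported with bootstrap confidence intervals.

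Section V.3, item 6 (Measures), Baseline Assessments, paragraph d, introduces the causal attribution measure with this statement: "Patients who perceive their acute health events as related to tobacco use are more likely to quit, as we found in our pilot trial". No effect size is given. The measure has two items and is scheduled at baseline only. Item 4 (Entry into study and Randomization) places baseline assessments before randomisation. The Measures overview says that baseline assessments are meant, among other things, to capture important predictors.

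Paragraph e describes the 7-item WI-PREPARE questionnaire, which "will be used to assess patient's likelihood of a relapse to smoking". Two of its items form the Heavy Smoking Index (HSI).

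**The concern.** The plan has already chosen covariate adjustment, so the only question is which covariates to use. For causal attribution the protocol cites its own data on a link with quitting. It collects the score from everyone before allocation and then gives it no part in the primary model. A belief about why one came to the ED cannot sensibly be read as a smoking characteristic, so the listed terms do not cover it. The randomisation described uses permuted blocks with no stratification factor, so the design does not balance the score either.

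What is at stake is a little power for each of the four main effects, and protection of each half-versus-half contrast against chance imbalance on a predictor that has already been measured. Validity is not at stake.

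**Working it through.** **Inputs from the documents** (Sample size and power calculations). Two-sided 5% level; a rate of 4.9% among those not given the component under test. The plan then states that "a total sample size of 860 participants will provide 80% power to detect a 5% increase in the abstinence rate", so the comparison is 4.9% against 9.9%. The split is equal, since "As each component is allocated to half the participants"; 1056 are enrolled.

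**Step 1: reproduce the stated sample size.** Pooled-variance formula with mean rate 0.074:

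n per level = [1.960 × √(2 × 0.074 × 0.926) + 0.842 × √(0.049 × 0.951 + 0.099 × 0.901)]² / 0.05² = (0.7256 + 0.3101)² / 0.0025 = 429.1, rounded up to 430.

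The total is 860, as stated, and power at 860 is 80.1%.

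**Step 2: put the unadjusted comparison on the logistic scale.** Log-odds ratio = ln(0.099/0.901) − ln(0.049/0.951) = 0.7573. SE at N = 860 is √{[2/(0.049 × 0.951) + 2/(0.099 × 0.901)]/860} = √(65.34/860) = 0.2756. The expected z is 0.7573/0.2756 = 2.747, which gives 78.5% power. At N = 1056 the expected z is 3.045 and power is 86.1%.

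**Step 3: add one prognostic covariate.** The marginal rates are held at 4.9% and 9.9%. The covariate's strength is assumed, either as an odds ratio (OR) for a 50/50 binary score or as an OR per SD for a normal score. The information matrix for intercept, component and covariate is integrated over the covariate distribution. Relative efficiency = (adjusted expected z / unadjusted expected z)².

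| Assumed score | Relative efficiency | Power, N = 860 (from 78.45%) | Power, N = 1056 (from 86.09%) | Fall in variance of risk difference |
|---|---|---|---|---|
| Binary, OR 1.5 | 1.0028 | 78.56% | 86.19% | 0.27% |
| Binary, OR 2 | 1.0078 | 78.76% | 86.35% | 0.77% |
| Binary, OR 3 | 1.0182 | 79.17% | 86.69% | 1.76% |
| Binary, OR 4 | 1.0269 | 79.51% | 86.97% | 2.59% |
| Continuous, OR 1.5 per SD | 1.0117 | 78.92% | 86.48% | 1.15% |
| Continuous, OR 2.0 per SD | 1.0362 | 79.86% | 87.27% | 3.48% |
| Continuous, OR 2.5 per SD | 1.0660 | 80.97% | 88.17% | 6.19% |

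In participants, the binary range is worth 0.0028 × 1056 ≈ 3 to 0.0269 × 1056 ≈ 28. The continuous range is worth 0.0117 × 1056 ≈ 12 to 0.0660 × 1056 ≈ 70.

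**Step 4: where the gain appears.** For a continuous score with OR 2.0 per SD and N = 860, the adjusted log-odds ratio is 0.7842 and the expected z is 2.7968, so the SE is 0.7842/2.7968 = 0.2804. That is larger than the unadjusted 0.2756. The power gain comes from the larger conditional effect. On the risk-difference scale it appears as a narrower interval: at OR 2.5 per SD the width falls by 1 − √(1 − 0.0619) ≈ 3%.

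**Step 5: cost in the planned model.** Expected events are 1056 × (0.049 + 0.099)/2 ≈ 78. The treatment terms are 4 main effects and 11 interactions, 15 in all. A simulation of 1056 participants gave relative efficiency of about 1.01 to 1.02 for a binary score (OR 2 to 3) and 1.01 to 1.08 for a continuous one (OR 1.5 to 2.5 per SD), in both the main-effects and the 15-term model. An irrelevant covariate gave 1.00.

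**The case against.** The case against is substantial, and much of it stands.

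- **Size.** The measure has two items and may behave more like the binary rows than the continuous ones. At N = 1056 that adds between 0.1 and 0.9 percentage points of power. This stands.
- **Comparator.** The table compares with a model without covariates, whereas the plan already adjusts for four groups of variables. The increment is smaller wherever the score overlaps with them. This stands.
- **Evidence.** The prognostic claim is one sentence. If it refers to the texting pilot in section C.2, that study had 60 participants and 9 + 4 = 13 self-reported abstainers at 3 months, without biochemical confirmation. The claim gives a reason to include the score but says nothing firm about its strength.
- **Parameters.** Fifteen treatment terms on about 78 events is already a heavy model. However, one further covariate cost essentially nothing in simulation even when it was irrelevant, so this does not defeat the point.
- **Validity.** Leaving out a prognostic covariate does not bias a randomised comparison. This stands.

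A reader might also infer that the relapse-risk score (WI-PREPARE) is left out. The documents do not show that. The smoking characteristics are not itemised and may include the WI-PREPARE or its HSI items, so the plan neither names nor excludes it. Nor do the documents support dropping age, sex or race/ethnicity as weaker terms, because nothing in them compares the prognostic value of the candidates.

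**Conclusion.** The point holds as a minor one about efficiency. The protocol identifies causal attribution as a predictor of quitting, measures it before randomisation, and does not list it in the primary model. The likely benefit is about 0.3% to 3% in efficiency for a binary score and about 1% to 7% for a continuous one. This rests on assumed odds ratios of 1.5 to 4 and 1.5 to 2.5 per SD respectively, on the plan's rates of 4.9% and 9.9%, and on comparison with an unadjusted model. The upper figures need a strongly prognostic continuous score, for which the documents offer no evidence.

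It would be too strong to call this free precision or a flaw in the primary analysis: the gain is small and conditional, one parameter is spent, and the planned test remains valid without it.

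**What to change.** Before any analysis by allocated component, add the baseline causal attribution score to the Aim 1 primary logistic model as one prespecified term. State how its two items are scored and coded. Keep the covariates already listed, and use the same adjusted model for the standardised risk differences and their bootstrap intervals. If the sponsor prefers to leave the score out, one sentence giving the reason would close the gap between the measures section and the analysis section.

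The cost is a change of SAP wording and one more model parameter. No new data, visits or participants are needed.

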hospital, incremental cost of longer follow-up booster phone call), costs related to QL use (i.e., counselor and patient time, cost of written materials, patient time on website), outpatient treatment costs, other medical costs, and patient costs (e.g., time, transportation). In evaluating a prior trial, we measured RA time for an ED-based BNI session. Clinician time costs will include wages, fringe benefits, and overhead. Cost of patient time will be calculated using the average wage rate in the geographic area. Relevant medication use will be obtained from the CPOE record; cost of medication will be based on the average of the current formulary price for the top 5 health insurers in Connecticut. Quitline costs: We will get number of counseling calls completed and costs of written materials used directly from QL records, then calculate costs of counselor and patient time related to the calls (both scheduled QL calls and calls to toll-free number). We will collect patient time on the website at 1 and 3 month assessments. We will exclude research costs because these would not be incurred if our intervention were standard care. Training and texting program setup costs will be excluded from the main analyses. Although these startup costs may be incurred, when distributed across many patients over many years, they would be negligible. We will collect information on training and setup costs and include in publications/sensitivity analysis, as these may be of interest to decision makers. Measuring Effectiveness. We will assess effectiveness (i.e., abstinence) biochemically at 3 months. With the MOST design, regression will estimate quit rates for the four potential intervention components, as well as the gains and losses that occur when combining them. Over time, abstinence reduces medical care utilization and improves quality of life. We will not track those savings in our patient cohort. Instead, we will update our adaptation of a popular model that simulates them.

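### Interactions are flagged on the log-odds scale, a poor match for absolute quit-rate synergy when components also work alone; a contrast in quit rates should be added

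*Combined protocol and SAP*

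**What the plan says.** In Section V.12, Analysis for Aim 1, three-month abstinence "will be compared between the presence and absence of each component using logistic regression", and "the model will include main effects for each of the 4 components as well as all 2, 3 and 4-way interactions". The interaction rule follows: "A p-value of 0.10 will be used as a guide to flag potentially important interactions which will be explored graphically". Synergy, and reversals in the direction of a component's effect, are named as the main targets of that exploration. The scale on which synergy is to be judged is not named. The same paragraph plans absolute estimates with bootstrap 95% confidence intervals, but only for the component contrasts: "Differences in proportions for the presence and absence of each component (i.e. main effects".

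Elsewhere the plan thinks in absolute quit rates. Under Sample size and power calculations, "we have chosen an absolute difference of 5% for the main effects of each component". The Economic analysis counts abstinent smokers at 3 months, expects the regression to estimate quit rates for the components "as well as the gains and losses that occur when combining them", and defines incremental cost-effectiveness as added cost over added effectiveness, using the 3-month quit rate and simulated QALYs.

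Three statements limit what the flag can do. The sample size section says the trial is not powered to detect interactions. The first cost-effectiveness pass sets out cost and adjusted quit rate for all 16 cells regardless of statistical significance. The Qualitative analysis uses important 2-way or 3-way interactions to choose arms from which to sample interviewees.

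**The concern.** The only interaction terms the plan specifies are product terms in a logistic model, so a p-value on them tests departure from multiplicative odds. The plan's design difference and its measure of benefit are percentage points of abstinence. At quit rates of roughly 5% to 20% the two scales can disagree, even in sign. A pair of components whose joint benefit exceeds the sum of their separate benefits in percentage points can have a log-odds interaction near zero, and a pair that simply adds has a negative one.

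At stake is whether the screen draws attention to the synergies that the Aim 1 paragraph says it particularly wants to find. No section plans an interaction contrast in quit rates that would make up for this.

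**Working it through.** **Inputs.** From the sample size section: "With a two-sided 0.05 significance level, and an average abstinence proportion of 4.9% in the absence of a component", a 5-point difference, 80% power, a total of 860, and 1056 enrolled. From the Aim 1 analysis: the logistic model, the 0.10 guide, and missing outcomes counted as smoking, so all 1056 are analysed. Assumptions: the 0.10 is two-sided (the plan does not say), no covariates, the other two components inactive.

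**The plan's own figure.** With p1 = 0.049, p2 = 0.099 and mean 0.074, n per level = [1.96·√(2·0.074·0.926) + 0.8416·√(0.049·0.951 + 0.099·0.901)]² / 0.05² = (0.7256 + 0.3101)² / 0.0025 ≈ 429.1. This rounds up to 430, or 860 in total, and the stated figure is reproduced.

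**Interaction contrasts.** Collapse to two components, with 1056/4 = 264 per cell and rates p00, p10, p01, p11.

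- Log-odds: L = logit p11 − logit p10 − logit p01 + logit p00, with SE = √Σ 1/[264·p(1−p)].
- Absolute: D = p11 − p10 − p01 + p00, with SE = √Σ p(1−p)/264.
- Flagged as synergy with probability Φ(−1.645 + contrast/SE), and as antagonism with Φ(−1.645 − contrast/SE).

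**Exact additivity, 4.9/9.9/9.9/14.9%.** The odds are 0.05152, 0.10988, 0.10988 and 0.17509. Interaction OR = 0.17509·0.05152/0.10988² = 0.747, so L = −0.291 with SE 0.443. Flagged as antagonism: Φ(−1.645 + 0.658) ≈ 16%, against 5% for D.

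**Rate at which the log-odds interaction is zero.** The OR for 4.9% to 9.9% is 2.133. Combined odds are 0.05152·2.133² = 0.2343, a rate of 19.0%. That is 4.1 points above the additive 14.9%, yet the log-odds contrast is zero.

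**A 5-point synergy on top, 4.9/9.9/9.9/19.9%.** OR = 1.06, L = 0.059, SE 0.436; flagged as synergy Φ(−1.645 + 0.134) ≈ 6.5%. On the absolute scale D = 0.05, SE 0.0382; Φ(−1.645 + 1.310) ≈ 37%.

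**Summary, including cases that favour the plan:**

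| Truth (p00/p10/p01/p11, %) | Interaction OR | Flagged as | Log-odds | Absolute |
|---|---|---|---|---|
| 4.9/9.9/9.9/14.9, additive | 0.75 | antagonism | 16% | 5% |
| 4.9/9.9/9.9/19.9, +5 synergy | 1.06 | synergy | 6.5% | 37% |
| 4.9/4.9/4.9/9.9, +5 only together | 2.13 | synergy | 41% | 52% |
| 4.9/4.9/4.9/14.9, +10 only together | 3.40 | synergy | 76% | 93% |

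**Sensitivity to the base rate.** The plan calls 4.9% the average rate without a component. If that average is taken over a second active component, (2.4 + 7.4)/2 = 4.9 and the additive cells are 2.4/7.4/7.4/12.4%. Additivity then gives OR 0.55, flagged as antagonism 29% of the time. A 5-point synergy (17.4% in the combined cell) gives OR 0.81, flagged as synergy 2% on log-odds against 43% on the absolute scale.

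**Sensitivity to the model.** A 20,000-run simulation of the saturated 16-cell model (66 per cell, effect coding, 0.5 added to counts) gives, as total flag rates on log-odds and absolute scales, 14% and 9% under additivity, 9% and 36% for the 5-point synergy, and 71% and 93% for 10 points only together. The plan does not state the coding. With dummy coding the 5-point synergy is flagged 8% and 17%.

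**The case against.** The strongest reply is that the flag selects nothing. It guides graphs and, through the Qualitative analysis, which arms to sample for interviews. Components enter the package on efficacy, cost-effectiveness and acceptability, and efficacy means all arms with a component against all arms without it. Where combinations are costed, the first pass looks at all 16 cells' quit rates with no significance gate. This stands, and it limits the consequence.

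Second, when both components work alone, the pair usually passes anyway. Simulating two-sided 0.05 main-effect tests (pooled z, 528 per level, no covariates), both components pass 95% of the time at 4.9/9.9/9.9/19.9%. A flag matters more for selection when synergy appears only together: at 4.9/4.9/4.9/9.9% both pass only 18% of the time, and there the log-odds flag reaches 41%. This also stands. A reader might infer from the scale mismatch that the plan will overlook synergy in general; the combination-only results contradict that.

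Third, logistic interaction terms are conventional, the main-effect test is itself logistic, and the plan discloses low power for interactions. Convention is a reason to keep the logit terms. But the disclosure does not cover a 16% rate of antagonism flags under exact additivity, nor a synergy flag rate close to chance for a 5-point synergy that the absolute contrast would flag 37% of the time with the same participants.

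**Conclusion.** The mismatch is real and the plan does not address it. Its interaction flag is on log-odds by inference from the model, its absolute estimates stop at main effects, and its yardsticks of benefit are absolute. In the case the trial is sized for, with 5-point effects from each component, the flag is poorly matched to absolute synergy: 6.5% against 37% for a 5-point synergy, and about 16% antagonism flags (nominal 5%) when effects simply add. For synergy seen only in combination it works, but less well.

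Two stronger conclusions are tempting and do not follow. One is that additive pairs will generally be declared antagonistic: at the reference rates about 84% are not so flagged, and the plan attaches no action to antagonism. The other is that the package will be chosen wrongly: the selection criteria and the ungated 16-cell pass do not depend on the flag. The point is therefore a worthwhile, inexpensive improvement to an exploratory analysis, not a fault in the primary comparison.

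The figures rest on the assumptions listed in the working, chiefly a two-sided 0.10, no covariates, two inactive components and Wald contrasts.

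**What to change.** In the Analysis for Aim 1:

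- State that synergy between components is judged on absolute abstinence rates.
- From the same logistic model, compute predicted abstinence proportions and report the six two-way differences of differences with bootstrap confidence intervals, averaging over the other two components. A 90% interval would match the existing 0.10 guide.
- Report these beside the logit interaction terms, and use both to decide which interactions to graph.

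The cost is about a paragraph of text. No new data are needed and the bootstrap is already planned. The downside is a few more chance flags: six contrasts at 0.10 would be expected to add at most 6 × 0.10 = 0.6 if no absolute interaction exists, fewer where they overlap with the logit flags. The change does not create power: at the reference rates about 63% of 5-point synergies would still go unflagged on the absolute scale, and the text should say so.
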